### 9.8.2 C-Peptide AUC Calculation

The area under the stimulated C-peptide curve (AUC) over the first 4-hour period of a mixed meal glucose tolerance test will be conducted at baseline and Months 5, 12, 18, and 24. The AUC at each visit is computed using the trapezoidal rule that is a weighted sum of the C-peptide values over the 240 minutes. The weighted mean C-peptide is AUC/240 (pmol/mL). AUC values will then be log-

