### **16.2.2. ANALYSIS OF SECONDARY EFFICACY ENDPOINTS**

#### **16.2.2.1. Continuous Secondary Efficacy Endpoints**

Observed and change from baseline for C-peptide AUC, HbA1c, total daily insulin dose, total daily basal insulin dose, total daily bolus insulin dose, and each of 4 antibodies will be summarized by treatment group and visit.

For the analysis of C-peptide AUC, a Mixed-effect Model for Repeated Measurements (MMRM) will be performed based on the PD analysis population using the observed-case data. This model will include the change from baseline

Author:	[name]	Version Number:	1.0
		Version Date:	28Mar2022
Template No.:	CS_TP_BS016 Revision 6	Reference:	CS_WI_BS005
Effective Date:	02Dec2019		

variable as the dependent variable, its baseline observed value as covariate, treatment group (active and placebo), visit, HbA1c, BMI, total insulin, potency assay, and treatment group-by-visit interaction as fixed effects. A backward stepwise variable selection process will be used to remove any non-relevant or highly correlated variables before fitting the final model. Restricted Maximum Likelihood (ReML) estimation will be used. An unstructured (UN) covariance structure will be used to model the within-patient error and an adjustment to the degrees of freedom will be made using the Kenward-Roger's approximation. In the event this model does not converge, the heterogeneous Toeplitz, heterogeneous first-order autoregressive (AR(1)), Toeplitz, and AR(1) covariance structures will be tested one after the other in the order listed here i.e., the heterogeneous Toeplitz covariance structure will be tested first and if this model converges, the other covariance structures will not be tested. If this model does not converge, then the heterogeneous AR(1) will then be tested. The same process will be repeated for each covariance structure one after the other as listed above until the model converges.

The Least Square (LS) mean estimates will be provided for each treatment group for each visit along with their standard error (SE). The difference of LS means between the treatment groups (active vs. placebo) and associated SE, two-sided 95% CI, and p-value will also be provided for each visit.

All remaining secondary endpoints (HbA1c, insulin, and auto-antibody levels) will be summarized univariately by generating summaries of the observed values and changes from baseline (both observed and percent changes) by study visit.

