## 6.2. BASELINE

Unless otherwise specified, baseline is defined as the last non-missing measurement taken prior to the first injection of study drug (including unscheduled assessments). In the case where the last non-missing measurement and the date

Author:	[name]	Version Number:	2.0
		Version Date:	23Nov2022
Template No.:	CS_TP_BS016 Revision 6	Reference:	CS_WI_BS005
Effective Date:	02Dec2019		

and time of the first injection of study drug coincide, that measurement will be considered pre-baseline, but adverse events (AEs) and medications commencing on the date and time of the first injection of study drug will be considered post-baseline.

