#### **16.2.2.1. Continuous Secondary Efficacy Endpoints – C peptide AUC**

For the primary analysis of C-peptide AUC, a Mixed-effect Model for Repeated Measurements (MMRM) will be performed based on the PD analysis population using the observed-case data. This model will include the change

Author:	[name]	Version Number:	2.0
		Version Date:	23Nov2022
Template No.:	CS_TP_BS016 Revision 6	Reference:	CS_WI_BS005
Effective Date:	02Dec2019		

from baseline variable as the dependent variable, its baseline observed value, age, and time from diagnosis to the first dose as covariates, treatment group (active and placebo), visit, HbA1c, BMI, total daily insulin divided by weight, potency assay, and treatment group-by-visit interaction as fixed effects. The fixed effects and covariates specified in SAP v1.0 were revised per the 22APR2022 memo-to-file to amend the SAP v1.0.

A backward stepwise variable selection process will be used to remove any non-relevant or highly correlated variables before fitting the final model. Restricted Maximum Likelihood (ReML) estimation will be used. An unstructured (UN) covariance structure will be used to model the within-patient error and an adjustment to the degrees of freedom will be made using the Kenward-Roger's approximation. In the event this model does not converge, the heterogeneous Toeplitz, heterogeneous first-order autoregressive (AR(1)), Toeplitz, and AR(1) covariance structures will be tested one after the other in the order listed here i.e., the heterogeneous Toeplitz covariance structure will be tested first and if this model converges, the other covariance structures will not be tested. If this model does not converge, then the heterogeneous AR(1) will then be tested. The same process will be repeated for each covariance structure one after the other as listed above until the model converges.

The Least Square (LS) mean estimates will be provided for each treatment group for each visit along with their standard error (SE). The difference of LS means between the treatment groups (active vs. placebo) and associated SE, two-sided 95% CI for each visit, and *p-value* will also be provided only for Visits at Day 150 and Day 360.

In addition, the following MMRMs for C-peptide AUC will be analyzed as exploratory analyses:

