- MMRM, based on the data locked for the primary analysis when the last subject completes the Month 5 study visit (Day 150), with the data at Visit 3/Day 1 included. A separate backward stepwise variable selection process will be performed.
- MMRM, based on the data locked for the primary analysis when the last subject completes the Month 5 study visit (Day 150), with the data at Visit 3/Day 1 excluded. A separate backward stepwise variable selection process will be performed.
- MMRM, based on the data locked for the supplemental analysis when the last subject completes the Month 12 study visit (Day 360), with the data at Visit 3/Day 1 excluded. A separate backward stepwise variable selection process will be performed.
- MMRM, based on the data locked for the supplemental analysis when the last subject completes the Month 12 study visit (Day 360), with the data at Visit 3/Day 1 excluded. The full model will be fitted directly without any variable selection process. The primary analysis performed in June 2022 for Day 150 reported results from the full model without any variable selection process, and with the data at Visit 3/Day 1 excluded.

Author:	[name]	Version Number:	2.0
		Version Date:	23Nov2022
Template No.:	CS_TP_BS016 Revision 6	Reference:	CS_WI_BS005
Effective Date:	02Dec2019		

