#### 16.2.2.2. Continuous Secondary Efficacy Endpoints – HbA1C

For the analysis of HbA1C, a Mixed-effect Model for Repeated Measurements (MMRM) will be performed based on the PD analysis population using the observed-case data. This model will include the change from baseline variable as the dependent variable, its baseline observed value, age, and time from diagnosis to the first dose as covariates, treatment group (active and placebo), visit, C-peptide AUC, BMI, total daily insulin divided by weight, potency assay, and treatment group-by-visit interaction as fixed effects.

The MMRM modeling and selection procedures described in section 6.2.2.1 will be used to select an appropriate model for this endpoint.

The Least Square (LS) mean estimates will be provided for each treatment group for each visit along with their standard error (SE). The difference of LS means between the treatment groups (active vs. placebo) and associated SE, two-sided 95% CI for each visit, and *p-value* will also be provided only for Visits at Day 150 and Day 360.

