## ALGORITHM FOR POTENCY ASSAY

As specified in the inclusion criteria 3 in the protocol, a subject is eligible for enrollment as the study participant, only if the subject “has a CD8+ T cell defect that is correctable in vitro by co-culture with immature dendritic cells loaded with the synthetic oligopeptide from Hsp60sp”.

Therefore, for the potency assay result of each patient on Visit 3/Day 1 (before the study treatment), should be imputed as the same as the corresponding potency assay result on Visit 1/Screening.

For potency assay results that are missing on any visits other than Visit 3/Day 1, no imputation will be performed.

---

Author: [name]

Version Number: 2.0

Template No.: CS\_TP\_BS016 Revision 6

Version Date: 23Nov2022

Effective Date: 02Dec2019

Reference: CS\_WI\_BS005

---

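### SAP v2.0 picks its MMRM covariates by backward selection on the outcome in about 24 subjects but reports p-values and 95% CIs as if the model were fixed; a nominal 5% test then runs at about 6 to 11%

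*Combined protocol and SAP*

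**What the plan says.** SAP v2.0 section 16.2.2.1 fits an MMRM to change in C-peptide AUC in the pharmacodynamic population, with unstructured covariance, REML and Kenward-Roger degrees of freedom. Beyond treatment, visit and their interaction there are seven covariates: baseline AUC, age, time from diagnosis, HbA1c, BMI, insulin divided by weight, and potency assay. Then: "A backward stepwise variable selection process will be used to remove any non-relevant or highly correlated variables before fitting the final model". No significance level, information criterion or collinearity limit is given, and no term is protected. Treatment differences get an SE and 95% CI at each visit, and p-values at Day 150 and Day 360. For HbA1c, section 16.2.2.2 adds, with a wrong section number: "The MMRM modeling and selection procedures described in section 6.2.2.1 will be used to select an appropriate model for this endpoint". Sections 16.2.2.3 and 16.2.2.4 do the same for insulin by weight and four autoantibodies.

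SAP v1.0 (28 March 2022) already had the selection step for C-peptide, followed by "two-sided 95% CI, and p-value will also be provided for each visit". For the rest: "All remaining secondary endpoints (HbA1c, insulin, and auto-antibody levels) will be summarized univariately". A memo-to-file of 22 April 2022 revised the covariates; unblinding was on 17 May 2022; v2.0 was signed off that December. v2.0 also records: "The primary analysis performed in June 2022 for Day 150 reported results from the full model without any variable selection process". It lists an unselected Day 360 fit among its exploratory analyses.

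On timing, v2.0 Appendix 1 copies the Screening potency result to Day 1 and adds: "For potency assay results that are missing on any visits other than Visit 3/Day 1, no imputation will be performed". Section 6.2 says "baseline is defined as the last non-missing measurement taken prior to the first injection of study drug". The C-peptide AUC, by Protocol Amendment 3 section 9.8.2, "will be conducted at baseline and Months 5, 12, 18, and 24". The v2.0 summary of changes defines a change from baseline at baseline itself, to let those rows into the MMRM.

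**The concern.** The removal tests use the same outcomes as the treatment test. The final SE treats the surviving covariates as if they had been chosen in advance, so it is too small for the procedure actually followed. Because the rule is not written down, two statisticians could follow the text and report different models.

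Two linked gaps affect the same estimate. Restoring the CD8+ regulatory function that the potency assay measures is what the product is meant to do (section 2.2), so a visit-level potency value would be a treatment-affected covariate. And Day 1 rows, where the change is zero for everyone, would disturb an unstructured fit.

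At stake is how the Day 360 results are read. Section 4.3 ties them to development milestones. A nominal p-value or 95% CI should still mean what it says.

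**Working it through.** **1. The plan's own figures.** Section 7.1: the chance of at least one event among 14 subjects at 12% incidence is 1 − 0.88^14 = 0.833, so at least 80% is right. Dropout: 21/0.9 = 23.3, rounded up to 24 (16:8). The SAP gives no operating characteristic for the selected MMRM, so there is none to reproduce.

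**2. Error after selection.** From the SAP: N of 24 or 21, 2:1 allocation, seven candidates, two-sided 5%, unstructured REML with Kenward-Roger. Assumed, because the SAP is silent: removal thresholds, covariate correlations, prognostic strength, visit correlation and complete data. Under no treatment effect, the covariate with the largest p-value is removed until all are at or below the threshold, and the treatment test is then read from the final model. Treatment, visit and interaction are kept. Rejection rates (%), Day 150 / Day 360, 2,500 trials per row, visit correlation 0.6, by removal threshold:

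| Setting | 0.05 | 0.10 | 0.20 | Full model |
|---|---|---|---|---|
| 16:8, noise covariates | 8.4 / 7.4 | 9.2 / 8.2 | 10.0 / 8.7 | 6.2 / 5.2 |
| 16:8, three prognostic (R² 0.3), correlation 0.3 | 9.9 / 8.9 | 10.4 / 9.6 | 10.4 / 9.6 | 6.2 / 5.2 |
| 16:8, noise, four varying by visit | 6.7 / 6.3 | 7.6 / 7.2 | 8.0 / 8.2 | 5.2 / 5.0 |
| 14:7, noise covariates | 7.7 / 7.4 | 8.8 / 8.6 | 9.9 / 10.0 | 5.6 / 5.5 |

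The Monte Carlo SE at 8% is √(0.08 × 0.92 / 2500) = 0.5 points. Over 80 cells (8 settings, 5 thresholds up to 0.50, 2 visits) the range is 6.3 to 10.4%, with 73 cells at 7 to 10%; the full model gives 4.8 to 6.2%. A second MMRM simulation (visit correlation 0.64, baseline AUC forced in all but one setting, 3,000 to 4,000 trials) gives 6.3 to 10.5% over 36 cells, 30 of them at 7 to 10%, against 4.5 to 5.9%. Single-visit ANCOVA gives 6.8 to 11.1% against 4.6 to 5.5%. Together: about 6 to 11%. With treatment forced, its size does not alter the removal tests, so a stated 95% CI covers about 100 − 11 = 89% to 100 − 6 = 94%.

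**3. Covariate timing.** Under section 6.2 the Screening potency is already the baseline value. A rule copying it to Day 1 is needed only if each visit row carries its own potency. That suggests visit-level entry but does not prove it. If so, let treatment shift potency by δ SD, let potency correlate ρ with the outcome within arm, and let the total treatment effect be zero. The adjusted treatment coefficient is then −ρδ outcome SDs; for δ = 2 and ρ = 0.4 it is −0.8. In an unselected single-visit ANCOVA (16:8, 4,000 trials) that setting rejected 20.3% of the time: 20.2% favouring placebo, 0.1% favouring the drug. At δ = 1 and ρ = 0.4 the split was 11.3% and 0.4%. The shifts and correlations are assumptions.

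In sections 16.2.2.2 to 16.2.2.4 C-peptide AUC is itself a covariate. HbA1c has six post-baseline visits to Day 360 (Days 30, 60, 90, 150, 270, 360; protocol Table 3), while the MMTT is done at two (Days 150 and 360). With visit-level AUC, 6 − 2 = 4 visits would drop from an observed-case fit, although LS means are promised for each.

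**4. Day 1 rows.** The exploratory list covers the Day 150 lock with and without Day 1 (both selected) and the Day 360 lock without Day 1 (selected and full). The combination left over, the Day 360 lock with Day 1 and selection, would be the main model. If so, two zero Day 1 means and seven zero slopes fit all 24 rows exactly. The REML log-likelihood then rises by (24 − 9)/2 = 7.5 per log unit fall in Day 1 variance. From variance 1 to 10⁻⁸ that predicts 7.5 × 18.42 = 138.2; a simulated data set went from −36.5 to +102.7, a rise of 139.2. The largest slope fell from 0.19 to 0, so covariate adjustment disappears.

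**The case against.** The strongest reply is that little depends on this. There is no primary efficacy endpoint, p-values are declared nominal, and the Month 5 analysis, which formed the main basis for the study objectives, reported the full model. The Day 360 full model is already listed. Selection was the only C-peptide MMRM in v1.0, so demoting it after unblinding is itself a post hoc choice. All of this stands. It limits the weight of the point, but it does not give the selected model's intervals their stated coverage.

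Four stronger readings are tempting and not supported:

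- That selection was brought in after the data were seen. It is in v1.0, before unblinding.
- That the HbA1c, insulin and antibody MMRMs and the Day 1 rule are known to be post hoc. They are absent from v1.0, but the April 2022 memo is not among the documents and may contain them. The protocol synopsis had also foreseen an MMRM for HbA1c, insulin and antibodies for data presentation.
- That visit-level potency would manufacture efficacy. With positive correlation the excess rejections fall almost wholly against the drug.
- That the main model cannot be fitted. Its use of Day 1 rows is inferred by elimination, and section 16.2.2.1 gives a fallback sequence of covariance structures for non-convergence. No error rate is claimed under those.

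**Conclusion.** The point holds as a fault of specification and inference in the supplemental efficacy analyses. Under assumed thresholds, the selected model's nominal 5% test runs at about 6 to 11%, mostly 7 to 10%, while the unselected full model stays near 5% provided treatment does not affect its covariates. The exact figure depends on a rule the SAP does not state. The covariate-timing and Day 1 points are conditional. If potency enters at visit level, is shifted by treatment and correlates with C-peptide, the treatment estimate is biased with or without selection. If Day 1 rows enter, the unstructured fit is degenerate and the result depends on the fallback structures. The safety conclusions and the reported Month 5 model are untouched by the selection step. This should be changed, but it does not overturn the trial.

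**What to change.** - Delete the selection step in SAP v2.0 section 16.2.2.1 and the references to it in 16.2.2.2 to 16.2.2.4, and exclude Day 1 rows.
- Make the unselected full model the headline at Day 150 and Day 360. State that HbA1c, BMI, insulin by weight and potency (and C-peptide AUC in 16.2.2.2 to 16.2.2.4) enter only at their baseline or screening value.
- Show the selected model, with its threshold and forced terms written down, as a sensitivity analysis. For C-peptide, identify selection as the v1.0 specification, with covariates as revised by the April 2022 memo.
- If the June 2022 fit and the listed full model used visit-level values, the baseline-only model is a new fit made after unblinding. Say so, and show the visit-level version as a sensitivity analysis.
- In the study report, state that this ranking was made after unblinding and reverses v1.0. Label features absent from v1.0 as post hoc unless the April 2022 memo shows that they predate 17 May 2022.

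The cost is SAP and report wording and at most one extra fit per endpoint. Compared with adjusting for baseline AUC alone, the Day 360 CI may be about 14% (N = 24) to 18% (N = 21) wider if the six further covariates are pure noise. That estimate comes from one simulation of 400 trials per sample size and has not been repeated.

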#### 16.2.2.2. Continuous Secondary Efficacy Endpoints – HbA1C

For the analysis of HbA1C, a Mixed-effect Model for Repeated Measurements (MMRM) will be performed based on the PD analysis population using the observed-case data. This model will include the change from baseline variable as the dependent variable, its baseline observed value, age, and time from diagnosis to the first dose as covariates, treatment group (active and placebo), visit, C-peptide AUC, BMI, total daily insulin divided by weight, potency assay, and treatment group-by-visit interaction as fixed effects.

The MMRM modeling and selection procedures described in section 6.2.2.1 will be used to select an appropriate model for this endpoint.

The Least Square (LS) mean estimates will be provided for each treatment group for each visit along with their standard error (SE). The difference of LS means between the treatment groups (active vs. placebo) and associated SE, two-sided 95% CI for each visit, and *p-value* will also be provided only for Visits at Day 150 and Day 360.

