#### **16.2.1.2. Change from Baseline in HbA1c**

HbA1c will be measured at the first screening visit and at each dosing and long-term follow-up visit as per the schedule of events (refer to protocol Table 3).

Change from baseline in HbA1c will be computed for baseline and for each post-baseline visit.

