#### 16.2.2.3. Continuous Secondary Efficacy Endpoints – Total Daily Insulin Divided by Weight

For the analysis of total daily insulin divided by weight, a Mixed-effect Model for Repeated Measurements (MMRM) will be performed based on the PD analysis population using the observed-case data. This model will include the change from baseline variable as the dependent variable, its baseline observed value, age, and time from diagnosis to the first dose as covariates, treatment group (active and placebo), visit, C-peptide AUC, BMI, HbA1C, potency assay, and treatment group-by-visit interaction as fixed effects.

The MMRM modeling and selection procedures described in section 6.2.2.1 will be used to select an appropriate model for this endpoint.

The Least Square (LS) mean estimates will be provided for each treatment group for each visit along with their standard error (SE). The difference of LS means between the treatment groups (active vs. placebo) and associated SE, two-sided 95% CI for each visit, and *p-value* will also be provided only for Visits at Day 150 and Day 360.

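### Six of the seven efficacy MMRMs give the outcome's own baseline one slope for all visits, so the Day 360 difference may keep part of a chance baseline imbalance; how much depends on which visits enter the fit

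*Combined protocol and SAP*

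**What the plan says.** SAP v2.0 specifies an MMRM on change from baseline for seven outcomes: C-peptide AUC (16.2.2.1), HbA1c (16.2.2.2), daily insulin divided by weight (16.2.2.3) and four autoantibodies (16.2.2.4).

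- **Baseline.** The HbA1c model takes "its baseline observed value, age, and time from diagnosis to the first dose as covariates". The other models do the same with their own baseline.
- **Interactions.** The HbA1c list ends with "potency assay, and treatment group-by-visit interaction as fixed effects". The insulin list is "visit, C-peptide AUC, BMI, HbA1C, potency assay, and treatment group-by-visit interaction as fixed effects" and the C-peptide list is "visit, HbA1c, BMI, total daily insulin divided by weight, potency assay, and treatment group-by-visit interaction as fixed effects". No baseline-by-visit term appears anywhere.
- **Covariance and selection.** "An unstructured (UN) covariance structure will be used to model the within-patient error", and "A backward stepwise variable selection process will be used to remove any non-relevant or highly correlated variables before fitting the final model". The own-baseline term is not exempted.
- **Testing.** The p-value "will also be provided only for Visits at Day 150 and Day 360".
- **Visits.** "HbA1c will be measured at the first screening visit and at each dosing and long-term follow-up visit". Protocol Table 3 puts HbA1c, antibodies and insulin usage at Days 1, 30, 60, 90, 150, 270 and 360. C-peptide AUC is measured at Days 1, 150 and 360 only. The potency blood draw has no Day 30 or Day 60 sample. Days 540 and 720 follow for all of these.

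The models use observed-case data. The SAP does not say whether C-peptide AUC, potency and the other covariates are baseline or visit values.

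**The concern.** For a change score with equal SDs, the regression slope on baseline at a visit is the correlation with baseline minus 1. If that correlation fades with time, the slope is near 0 at Day 30 and well below 0 at Day 360. A single slope cannot fit both. An unstructured fit gives most weight to the visits with least residual variance, which are the early ones, so Day 360 is under-adjusted.

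Day 360 is one of only two visits with a p-value, and SAP 4.3 ties it to decisions on development milestones. With 16 against 8 subjects, chance imbalance at baseline is not small. What is at stake is a single reported difference that carries part of that imbalance, and some lost precision. Visit-specific slopes would remove both using data already collected.

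**Working it through.** **The plan's own figure.** There is none for this point. The only current design calculation is for safety: 1 − 0.88^14 = 0.833, which meets the stated 80%, and 21/0.9 = 23.3, rounded up to 24. Neither depends on the MMRM.

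**Inputs.** From the documents: allocation 16:8, the visit days, unstructured covariance, and p-values at Days 150 and 360. Assumed, because the documents give no figures: SD of 1 at every visit, and a correlation between two time points d days apart of λ + (1 − λ)exp(−d/τ), with τ set by the Day 30 correlation. The own baseline is the only covariate and data are complete.

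**Formulas.**
- Slope at visit t: b_t = corr_t − 1.
- Common slope: the average of the b_t with weights R⁻¹1/(1′R⁻¹1), where R is the residual covariance given baseline.
- Share of imbalance left at Day 360: |b_360 − b_common|.
- Variance ratio against visit-specific slopes: 1 + (b_360 − b_common)²/(1 − corr_360²).

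**Results.**

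| λ, Day 30 corr. | Day 360 corr. | b_360 | b_common, six visits | Left, six visits | Variance ratio | Left, Days 150 and 360 only | Variance ratio |
|---|---|---|---|---|---|---|---|
| 0.7, 0.9 | 0.70 | −0.298 | −0.159 | 0.14 | 1.04 | 0.02 | 1.00 |
| 0.5, 0.9 | 0.53 | −0.466 | −0.173 | 0.29 | 1.12 | 0.08 | 1.01 |
| 0.3, 0.9 | 0.41 | −0.590 | −0.181 | 0.41 | 1.20 | 0.13 | 1.02 |
| 0.3, 0.8 | 0.31 | −0.688 | −0.375 | 0.31 | 1.11 | 0.06 | 1.00 |
| 0, 0.9 | 0.28 | −0.718 | −0.189 | 0.53 | 1.30 | 0.20 | 1.04 |

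Worked row (λ = 0.3, Day 30 correlation 0.9): left = 0.590 − 0.181 = 0.409; ratio = 1 + 0.409²/(1 − 0.41²) = 1.20.

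**Size of the shift.** The SD of the chance imbalance is √(1/16 + 1/8) = 0.433 baseline SD. A one-SD imbalance moves the six-visit Day 360 difference by 0.433 × 0.14 = 0.06 to 0.433 × 0.53 = 0.23 baseline SD. If the HbA1c SD were 1.2 points (assumed), that is about 0.07 to 0.27 points.

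**Simulation, 16:8, six visits.**
- Same five patterns: 14–52% of the imbalance is left, against 0–2% with visit-specific slopes. Variance is 1–25% larger.
- Four other patterns (Day 360 correlations 0.76, 0.58, 0.45, 0.41): adding the interaction takes the Day 360 SE from 0.294 to 0.286, 0.381 to 0.361, 0.418 to 0.389 and 0.449 to 0.407. The shift from a one-SD imbalance is about 0.3–0.5 of the SE.
- Constant slope: nothing is left over, and the SE goes from 0.313 to 0.315.
- Type I error over all randomisations is 4.5–5.6%. When imbalance exceeds 0.6 baseline SD (17% of randomisations, first five patterns) it is 7–12%, against 5–6% with the interaction.

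**Simulation, Days 150 and 360 only** (same four patterns): SE 0.290 to 0.290, 0.369 to 0.366, 0.383 to 0.381 and 0.407 to 0.401.

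**The case against.** The strongest objection is that the early visits may never enter the fit. The HbA1c, insulin and antibody models all list C-peptide AUC and potency as covariates on observed-case data. SAP Appendix 1 fills in potency for Day 1 and forbids imputation at every other visit, a rule that makes most sense if potency is a visit value. If C-peptide AUC is also a visit value and survives selection, Days 30, 60, 90 and 270 drop out and the small two-visit figures apply. This stands. But the SAP does not settle which values are used, and selection may remove C-peptide AUC, so the larger effect cannot be ruled out.

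It is also fair that a main-effect baseline is a legitimate specification, that every correlation here is assumed, and that the calculations omit the other covariates, dropout and selection. These endpoints are exploratory with nominal p-values, and the primary endpoints are safety outcomes without testing. All of this limits the weight of the point. It does not remove it, because the term costs almost nothing when slopes are constant.

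A reader might infer that the planned tests are invalid. They are not: averaged over randomisation the estimate is unbiased and type I error is about 5%. The problem is conditional on the imbalance that happens to occur. A reader might also infer that all seven models, C-peptide AUC included, force one slope from Day 30 to Day 360. C-peptide AUC has no visit between Day 1 and Day 150, so for that model only the small effect applies.

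**Conclusion.** The point holds in a limited form. Six models (HbA1c, insulin per weight, four antibodies) let the treatment effect vary by visit but hold the baseline slope fixed, and they leave the baseline term open to removal.

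- **All six visits in the fit, correlation fading:** 14–53% of any baseline imbalance stays in the Day 360 difference, and its variance is up to about 25–30% larger.
- **Only Days 150 and 360 contributing**, as in the C-peptide AUC model: 2–20% stays and variance is 0–4% larger.
- **Constant slope:** no loss.

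These sizes rest on assumed correlations and equal SDs. The finding concerns precision and conditional bias in exploratory results. It does not touch the overall error rate, the safety objective or the sample size.

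**What to change.** SAP 4.4 provides for an amendment before the Month 24 lock, when Days 540 and 720 will lengthen the span that one slope must cover. In that amendment, for 16.2.2.2 to 16.2.2.4, and for consistency 16.2.2.1:

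1. Include the outcome's own baseline and its interaction with visit, and exempt both from backward selection.
2. Exclude Day 1 rows. SAP v2.0 defines change at baseline so that these rows can enter an MMRM, but that change is 0 for everyone. By reasoning (not simulated), such rows pull a common slope towards 0 and leave an unstructured covariance with a zero-variance visit.
3. Keep the existing models as sensitivity analyses.
4. Label the change as made after unblinding, which SAP 4.2 dates to 17 May 2022.
5. State whether C-peptide AUC, potency and the other covariates are baseline or visit values, since the size of the effect turns on this. Correct the cross-reference to section 6.2.2.1, which should read 16.2.2.1.

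The cost is about one degree of freedom per visit. In simulation the Day 360 SE rose by about 1% with constant slopes (0.315/0.313), and variance at Days 60 and 90 rose by at most about 3%. The cost alongside the full covariate list was not examined. The other cost is a further post-unblinding change to nominal p-values, which the retained models make visible.
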